1. TITLE PAGE

| | |
|---------------------------------|---|
| Study Title: | A Multi-Center, Randomized, Double Masked, Placebo Controlled Clinical Study to Assess the Safety and Efficacy of BRM421 Ophthalmic Solution in Subjects with Dry Eye using a Controlled Adverse Environment (CAE®) Model |
| Investigational Product: | BRM421 Ophthalmic Solution |
| Indication Studied: | Dry Eye Syndrome (DES) |
| Brief Description: | This is a multi-center, double-masked, randomized, vehicle-controlled, phase 2 CAE study in approximately 150 subjects. (75 per treatment arm). |
| Name of the Sponsor: | BRIM Biotechnology, Inc. [name] |
| Protocol Identification: | BRM421-16-C001-PR amendment 1,03 February 2017 |
| Development Phase: | 2 |
| Study Initiated: | 07 February 2017 (first subject first visit) |
| Study Completed: | 20 May 2017 (last subject last visit) |
| NCT number: | NCT03066219 |
| Document Date | IRB approval on 06 February 2017 |
| Date of Report: | 11 September 2019 |

Statement of Compliance with
Good Clinical Practice

This study was performed in compliance with the ethical principles of the Declaration of Helsinki and the International Conference on Harmonisation (ICH) Harmonised Tripartite Guideline for Good Clinical Practice (GCP).

Confidentiality Statement

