3. STUDY PROTOCOL

This was a multi-center, double-masked (participants and research team), randomized, placebo-controlled, phase 2 study conducted between February 2017 and May 2017 at 2 sites in the United States (Andover Eye Associates and Central Maine Eye Care). This study (ClinicalTrials.gov identifier: NCT03066219) was performed in compliance with the ethical principles of the Declaration of Helsinki and the International Conference on Harmonisation (ICH) Harmonised Tripartite Guideline for good clinical practice (GCP). Institutional Review Board (IRB)/Ethics Committee approval was obtained. All potential subjects provided written informed consent before screening.

After the screening visit, eligible subjects entered a one-week run-in period to receive preservative-free placebo solution bilaterally three times daily (TID) to minimize the placebo effect. Subjects that exhibited improvements in symptoms of dry eye syndrome (DES) at the end of the run-in period, relative to screening values, were disqualified. Eligible subjects were subsequently randomized in a 1:1 ratio to receive placebo or BRM421 Ophthalmic Solution three times daily (TID) in each eye for total 4 weeks, and the efficacy and safety assessments were performed at 1, 2 and 4 weeks after treatment.

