4. STATISTICAL ANALYSIS PLAN

The primary efficacy analyses, including FCS and ocular discomfort score, were performed using the last observation carried forward (LOCF) imputation method of the intent-to-treat (ITT) population at week 4 for missing values. The treatment effect in each group was calculated by change from baseline in pre- to post-controlled adverse environment (CAE) mode.

The difference from baseline in pre- to post-CAE values for active treatment was tested versus placebo using a two-way ANCOVA model adjusting for baseline at $\alpha = 0.05$. A Wilcoxon rank sum test and a two-sample *t*-test were also assessed where appropriate.

The continuous and ordinal secondary efficacy variables were analyzed with an ANCOVA model adjusting for baseline and also evaluated with a two-sample *t*-test comparing active treatment to placebo. No imputation was performed for secondary efficacy variables.

All analyses were performed using SAS software, version 9.4 (SAS Institute Inc., Cary, NC, USA).

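### Secondary variables get two observed-case tests with no governing one, and earlier visits do not inform a later comparison when a value is missing

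*Combined protocol and SAP*

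**What the plan says.** For the secondary variables, section 4 (Statistical Analysis Plan) reads: "The continuous and ordinal secondary efficacy variables were analyzed with an ANCOVA model adjusting for baseline and also evaluated with a two-sample *t*-test". It adds: "No imputation was performed for secondary efficacy variables". It does not name the analysis set for these variables, the visits compared, the alpha level, or which of the two tests decides.

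For the primary variables, the same section uses the "last observation carried forward (LOCF) imputation method of the intent-to-treat (ITT) population at week 4 for missing values", followed by a baseline-adjusted ANCOVA at 0.05. A rank-sum test is mentioned in that part of the text, for use where appropriate.

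Section 3 (Study Protocol) says that "the efficacy and safety assessments were performed at 1, 2 and 4 weeks after treatment". No model that combines the three visits is described anywhere. The title page gives the size: "phase 2 CAE study in approximately 150 subjects. (75 per treatment arm").

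**The concern.** Two features of the secondary analysis are weak.

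- **Observed cases without a longitudinal model.** An ANCOVA or t-test at one visit, with nothing imputed, uses only subjects with a value at that visit. Someone seen at weeks 1 and 2 but missing at week 4 drops out of the week 4 comparison, and the earlier values do nothing to correct for the absence. If subjects leave because they were doing badly, and do so more in one arm, those who remain in that arm look too good. The primary analysis handles the same absence by LOCF. Primary and secondary results could therefore diverge through missing-data handling alone.
- **Two p-values per variable.** With no governing test named, a reader cannot tell which result counts when the two disagree. If either may be cited, the error rate per variable exceeds the nominal level.

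**Working it through.** The documents give no effect size, SD, power, missing rate or correlation for any secondary variable. The only figure to reproduce is the sample size: 2 x 75 = 150, which agrees. What follows gives scale under stated assumptions.

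**1. Two tests per variable**

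Inputs: 75 per arm (title page). Assumed: two-sided 0.05 for each test (section 4 gives 0.05 for the primary test only and does not state sidedness), a t-test on change from baseline, and baseline-to-outcome correlation r of 0.3 to 0.7.

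Scale baseline b and outcome y to unit variance.
- ANCOVA compares the arms on e = y - r·b, with variance 1 - r².
- The t-test compares them on y - b = e - (1 - r)·b, with variance 2(1 - r).
- The covariance of the two is 1 - r², so the test statistics correlate at (1 - r²)/√[(1 - r²)·2(1 - r)] = √[(1 + r)/2].

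The chance that at least one is significant under the null is 1 - P(|Z1| < 1.96 and |Z2| < 1.96) for a bivariate normal with that correlation:

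| r | Correlation of tests | Either positive, formula | Either positive, simulated (10,000 trials) |
|---|---|---|---|
| 0.3 | 0.806 | 7.8% | 7.8% |
| 0.5 | 0.866 | 7.3% | 7.1% |
| 0.7 | 0.922 | 6.8% | 6.8% |

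Each test alone stayed at 4.7 to 5.0% in the simulation. A separate simulation gave 6.7 to 7.6% for either. The rate is thus about 7 to 8% per variable.

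**2. Bias when values are missing**

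Assumed: 75 per arm, unit variances, all pairwise correlations 0.6 among baseline and weeks 1, 2 and 4. Higher scores are worse. True differences are -0.2, -0.3 and -0.45 SD at weeks 1, 2 and 4. A fraction m is missing at week 4. Active-arm dropout is random with probability m. Placebo dropout has probability 2m·Φ(1.5 x week 2 score), which averages m but falls on those doing worse. There were 4,000 trials per row.

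| m | Observed-case ANCOVA | LOCF ANCOVA | Week 4 predicted from baseline and weeks 1 and 2 |
|---|---|---|---|
| 5% | -0.442 | -0.456 | -0.451 |
| 10% | -0.429 | -0.459 | -0.447 |
| 20% | -0.411 | -0.474 | -0.451 |

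The last column stands in for a likelihood-based repeated-measures analysis.

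Observed-case bias against -0.45:
- 5% missing: 0.450 - 0.442 = 0.008 SD
- 10% missing: 0.450 - 0.429 = 0.021 SD
- 20% missing: 0.450 - 0.411 = 0.039 SD

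A separate check under arm-dependent dropout reached -0.40 at 20%, a bias of 0.05 SD. The working range is therefore 0.01 to 0.05 SD. For comparison, the observed-case estimate had a standard error of 0.132 to 0.148 SD, so even 0.05 is about a third of one standard error (0.05/0.148 = 0.34). Using the earlier visits removed nearly all of the bias. LOCF erred in the other direction, by 0.006 to 0.024 SD.

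**The case against.** The strongest case against is that this is a phase 2 study, that no confirmatory claim or alpha is attached to the secondary variables, and that ANCOVA is listed first with the t-test as an addition. On that reading ANCOVA already leads and no error rate is inflated. The text is also a short past-tense summary, and a fuller plan may state the set, the visits and the lead test. Both points have force. They limit the matter to a cheap improvement, but section 4 as supplied still leaves the governing test open.

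Several stronger readings are tempting, and the documents do not support them.

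- **A non-ITT or completers-only set.** The secondary set is not named. Observed cases within the ITT population fit the text, and the subjects differ from the primary set only where values are missing.
- **Repeated data thrown away.** Week 4 is tied to the primary analysis only. Separate analyses at each visit may have used every observed value. The accurate statement is that earlier values do not inform a later visit's comparison.
- **Absence of imputation as the fault, or LOCF as the better standard.** An MMRM imputes nothing either, and LOCF was biased too in the table above.
- **A recoverable loss of power.** At an assumed 0.46 SD effect, 10% missing lowers power from 79.9% to 75.6%. With weeks 1 and 2 observed in everyone, using them brings it only to 76.0 to 76.8% (correlations 0.3 to 0.8). The gain is 0.4 to 1.2 of about 4 points; the rest is information that was never collected.
- **Precision lost through the t-test.** On change it needs 2/(1 + r) times the ANCOVA sample (1.33 at r = 0.5, 1.54 at r = 0.3), but nothing is lost while ANCOVA is also run.
- **Ordinal scores wrongly analysed.** Baseline-adjusted ANCOVA on ordinal scores with about 75 per arm is common practice, and a different model is largely a preference. The rank-sum sentence does not clearly exclude secondary variables.

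**Conclusion.** The point holds in a limited form. Each secondary variable has two tests with no stated precedence, run on observed values, with no model that lets weeks 1 and 2 inform a later comparison.

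The two sizes rest on different assumptions. The 7 to 8% error rate per variable does not depend on missing data. It does require that either test could support a claim, that the t-test is on change, and that the baseline correlation is 0.3 to 0.7. The bias of 0.01 to 0.05 SD requires 5 to 20% missing and dropout that depends on earlier response differently by arm. Its direction follows the arm that loses its poorer responders. The documents report no missing counts, so the true size is unknown and may be nil.

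This is worth correcting because the better method is specific and inexpensive. It is not evidence that any reported secondary result is wrong.

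**What to change.** - **Continuous secondary variables measured at weeks 1, 2 and 4:** make one MMRM the governing analysis, on all randomised subjects with any post-baseline value. Terms: treatment, visit, treatment-by-visit, baseline, baseline-by-visit and site.
- **Variables measured once, and ordinal scores:** keep the baseline-adjusted ANCOVA as the single governing test. A rank-based or proportional-odds analysis is an optional sensitivity check.
- **All secondary variables:** drop the two-sample t-test as a second p-value. State the analysis set and the visits compared, and report missing counts by arm and visit so that a reader can judge whether the missing-data part matters.

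Section 3 gives the visits for assessments in general, not by variable, so the list of variables that qualify for the MMRM must be confirmed first. The MMRM relies on missingness being explained by the observed data; it does not protect against dropout that depends on unseen values.

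The cost is modest programming on existing data. The last visit was on 20 May 2017 and the report is dated 11 September 2019, so the re-analysis must be labelled post hoc and shown beside the reported results.
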